8.2 Multicenter studies

The planned study centers are located in the U.S.A., Turkey, the Netherlands, and Germany. The study will be conducted at up to 5 study centers in total. Analysis will be performed on the combined data from all study centers.

8.3 Multiple comparisons and multiplicity

There will be no adjustments for multiplicity.

8.4 Derived and computed variables

8.4.1 First and last study treatment

Day 1, Week 1 is the day of first study treatment, the day prior to 1st study treatment is Day -1. The last study treatment will be at the latest at Week 24 of the Treatment period.

8.4.2 Study treatment exposure

For patients who continued study treatment until end of the study SOBI003-001, study treatment exposure in weeks will be calculated as ([date of last visit attended – date of 1st infusion of study treatment] + 1) / 7, rounded to the nearest decimal.

For patients who stopped study treatment during the course of the study, study treatment exposure in weeks will be calculated as ([date of last infusion + 7 days – date of 1st infusion of study treatment] + 1) / 7, rounded to the nearest decimal.

8.4.3 Baseline and change from baseline

Baseline is defined as the last available assessment prior to 1st infusion of study treatment.

Change from baseline = (post-baseline value – baseline value).

8.4.4 Age

Age (months) will be derived as date of 1st infusion – birth date. Since only month and year of birth are captured, “15” will be used as day of birth for calculation.

8.4.5 Adverse event duration

If times are available and if the duration is less than 24 hours, the duration will be calculated as (end date/time – start date/time) and presented in hh:mm. If at least 1 time is missing or if the duration is at least 24 hours it will be calculated as (end date - start date)+1 and presented in days.

In case of partial/missing start or end date duration will not be calculated.

8.4.6 Time since study treatment administration for adverse event

If times are available and if time to onset is less than 24 hours, the time will be calculated as (start date/time – first/last administration date/time) and presented in hh:mm. If at least 1 time is missing or if the time to onset is at least 24 hours then it will be calculated as (start date – first/last administration date) + 1 and presented in days.

In case of partial/missing AE start date the time since study treatment administration will not be calculated.

8.4.7 Body mass index (BMI)

Body mass index (kg/m²) will be derived as weight (kg)/(height(cm)/100)² and rounded to the nearest decimal.

8.4.8 Dose received

At each visit from Week 1 onwards, the actual infusion volume administered, including the added SOBI003 volume is reported in the eCRF. Total infusion volume to be administered is 100 mL for patients with a bodyweight < 25 kg and 250 mL for patients with a body weight \geq 25 kg.

Dose received will be calculated at each visit as (added SOBI003 volume * 20), rounded to the nearest decimal and presented in mg.

Dose received will also be calculated at each visit in mg/kg as (added SOBI003 volume * 20 / bodyweight, rounded to the nearest decimal.

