SOBI003 concentrated solution is diluted with NaCl 0.9% infusion solution prior to administration. For a bodyweight < 25 kg, the targeted total infusion volume is 100 mL. For a bodyweight \geq 25 kg, the targeted total infusion volume is 250 mL. If the infusion bag contains an overfill volume, the infusion should continue until the infusion bag is emptied.

The final concentration of SOBI003 in the infusion bag will be calculated based on the added volume of SOBI003 to the infusion bag, and the total volume in the infusion bag.

A slower infusion rate is applied for the initial hour for all dose cohorts, targeting the delivery of 3% of the total dose/infusion volume. The infusion rate will be set to deliver the remaining 97% of the dose/infusion volume over the next 3 hours. Infusion rate schedules are provided in a separate IMP manual.

In case of occurrence of infusion reactions, the infusion duration may be prolonged up to 24 hours at the discretion of the investigator.

The drug accountability records will capture sufficient details to verify the amount of SOBI003 administered at each infusion occasion.

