14.1 Drug exposure

Upon provision of signed informed consent, patients are assigned a patient number and allocated to a dose cohort in strict consecutive order. Thus, the first 3 enrolled patients are assigned to Cohort 1 and administrations of SOBI003 at 3 mg/kg/week; for Cohorts 2 and 3, dose levels of 10 mg/kg/week and 20 mg/kg/week are planned.

At the time of the 1st SOBI003 infusion, the patient should not have any clinically significant evidence of an ongoing infection, or an ongoing treatment with antibiotics. In such cases, the 1st infusion should be postponed until the infection has resolved.

SOBI003 is administered as weekly i.v. infusions over a period of time of 4 hours. The study treatment period comprises 24 weekly infusions. For each weekly visit, date and time of administration will be recorded in the eCRF, as well as reasons for infusion stop (if any), dose level, SOBI003 volume, total infusion volume administered, and dosing action taken (e.g., “withdrawn”). All data will be listed.

In addition, actual dose received in mg, actual dose level received in mg/kg (see Section 8.4.8), and study treatment exposure in weeks will be calculated (see Section 8.4.2). These data will be listed and summarized.

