15.5.4 PK parameters derivation

The PK parameters will be estimated as follows:

- The apparent C_{max} and the corresponding T_{max} will be read directly from the concentration-time plot (observed data).
- AUC_{last} is calculated using the log-linear trapezoidal interpolation rule for intravenous model.

Terminal elimination parameters, elimination rate constant and $t_{1/2}$, will be derived as below if sufficient data are available.

The terminal elimination rate constant (λz) will be determined by log linear regression obtained on at least the 3 last quantifiable concentrations and will not include C_{max} ;

$t_{1/2}$ is calculated by the program as $\ln 2/\lambda z$;

The AUC_{0-inf} is calculated by the program as:

$AUC_{0-inf} = AUC_{last} + AUC_{extrap}$ where last is the sampling time point of the last measurable concentration (t_{last}). AUC_{extrap} is calculated by the program as: $C_{last}/\lambda z$, where C_{last} is the observed concentration at time t_{last} and λz is the elimination rate constant during the apparent terminal elimination phase; AUC_{0-inf} will only be presented for patients with a reliable λz ;

For single-dose, CL is calculated by program as (dose/ AUC_{0-inf}) and for multiple-dose, CL is calculated by program as (dose/ AUC_{0-168h});

V is calculated by the program as (dose/ AUC_{0-inf})/ λz ;

Fluctuation % is calculated by the program as $100 \times ((C_{max} - C_{min})/C_{avg})$.

The following PK acceptance criteria will be considered to when the reliability of elimination parameters are assessed:

- Number of points to calculate λz is greater than or equal to 3 excluding C_{max} point;
- Interval for calculation of λz is longer than half-life;
- The adjusted square of the correlation coefficient (Rsquare adjusted) for the goodness of fit of the regression line through the data points must be ≥ 0.75 ;
- $AUC_{extrap} \leq 30\%$.

However, less strict acceptance criteria may be applied, in exceptional cases, since the number of PK samples are limited. PK parameters may be calculated and reported even if the strict criteria are not fulfilled. When PK parameters are based on less strict criteria, this will be described on an individual level.

Accumulation ratios will be calculated as ratio of PK parameters (C_{max} , C_{min} , $C_{End\ of\ inf}$, AUC_{0-168h}) for the last vs 1st dose.

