15.7 Assessment of Dose Proportionality for SOBI003

Exploratory dose proportionality will be analyzed with the method originally described by Gough et al. (1995) (14) and modified as described by Smith et al. (2000) (15) and further adapted by Hummel et al. (2009) (16).

$C_{end\ of\ inf}$, AUC_{0-168h} will be analysed, and depending on the results other parameters may be analysed such as C_{max} , C_{min} and AUC_{0-inf} may also be analyzed. The general model $\log(C_{max}, C_{min}, C_{end\ of\ inf}, AUC_{0-168h}, AUC_{0-inf})$ for all doses and cycles where available) = $\mu + \beta \log(\text{dose})$ will be used to investigate the null hypothesis ($H_0: \beta=1$). Dose-proportionality will be rejected if the 90% CI of the estimated slope falls outside the critical interval. Patient's weight or age may be included as covariate.

The critical interval will be calculated as follows:

First the ratio (r) of the highest dose level to the lowest dose level will be calculated.

The lower limit of the critical interval will be calculated as: $\text{Log}(0.5)/\text{log}(r) + 1$.

The upper limit of the critical interval will be calculated as: $\text{Log}(2.0)/\text{log}(r) + 1$.

r value is based on the ratio between highest and lower dose levels of SOBI003 and equals to $20 / 3 \text{ mg/kg} = 6.667$

Thus, critical interval to declare dose linearity will be 0.63 to 1.37 for 90% CI of the slope estimate.

Additionally, PK parameters C_{\max} , C_{\min} , $C_{\text{End of inf}}$, AUC_{0-168h} , $AUC_{0-\infty}$ with total dose and body weight adjusted dose will be investigated using Pearson correlation analysis to estimate which type of dosing has an effect on pharmacokinetics of SOBI003.

The FISHER option in the PROC CORR statement will be used to estimate confidence limits and p-values for Pearson correlation coefficients based on Fisher's z transformation. Alpha value and a null hypothesis value will be specified for 95% two-sided CI.

The formula for sample Pearson product-moment correlation is:

$$r_{xy} = \frac{\sum_i (x_i - \bar{x})(y_i - \bar{y})}{\sqrt{\sum_i (x_i - \bar{x})^2 \sum_i (y_i - \bar{y})^2}}$$

Fisher z transformation is calculated as $z = 0.5 \log_e \left(\frac{1+r}{1-r} \right)$

CI's in addition to p-value will be calculated to demonstrate the validity of correlation.

Dose proportionality will also be explored graphically with plots of C_{\max} , AUC_{last} and AUC_{∞} vs body weight adjusted dose (mg/kg) or total dose (mg).

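### SAP 8.4.8 computes the dose received from the volume put into the bag, so an infusion abandoned part-way is credited as a full dose

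*SAP*

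**What the plan says.** SAP 8.4.8 gives the rule in mg: "Dose received will be calculated at each visit as (added SOBI003 volume * 20), rounded to the nearest decimal and presented in mg". The mg/kg version is the same product divided by bodyweight. The section first notes that the volume actually infused is recorded in the eCRF, and gives the intended totals of 100 mL (below 25 kg) or 250 mL (25 kg and above). It then uses neither in the formula.

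SAP 14.1 collects these items for each weekly visit: "reasons for infusion stop (if any), dose level, SOBI003 volume, total infusion volume administered". It goes on to say that "actual dose received in mg, actual dose level received in mg/kg (see Section 8.4.8), and study treatment exposure in weeks will be calculated", and that these are listed and summarized. The summary is Table 14.3.4.7.1 (Extent of Exposure).

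Protocol 7.4.6 fixes the meaning of added volume: "The final concentration of SOBI003 in the infusion bag will be calculated based on the added volume of SOBI003 to the infusion bag", together with the total volume in the bag. It also says: "The drug accountability records will capture sufficient details to verify the amount of SOBI003 administered at each infusion occasion". On overfill: "If the infusion bag contains an overfill volume, the infusion should continue until the infusion bag is emptied".

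**The concern.** Concentrate added, multiplied by its 20 mg/mL strength, is what the pharmacy prepared. It equals what the child received only if the bag was emptied. The SAP expects that some infusions may stop, because it records the reason, but the dose derivation cannot register one. SAP section 12 plans no compliance analysis, so no other summary would show the shortfall.

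This is a first-in-human study with safety at different dose levels as its primary objective. If an infusion is abandoned because of a reaction, the exposure listing and table would pair that visit with a full dose. The adverse event tables are by cohort and would not change.

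There may also be an effect on pharmacokinetics. SAP 15.5.4 divides a dose by an AUC ("For single-dose, CL is calculated by program as" dose over AUC to infinity, with the 0–168 h AUC for multiple dosing) and does not say which dose. SAP 15.7 examines PK parameters "with total dose and body weight adjusted dose will be investigated using Pearson correlation analysis". A total dose in mg is not a cohort level, and 8.4.8 is the only place where the SAP derives a dose in mg.

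**Working it through.** The plan gives no figure of its own to reproduce, so the check compares the SAP formula with the delivered dose under the protocol's infusion profile.

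**Inputs**
- Concentrate strength: 20 mg/mL (Protocol 7.4.2).
- Standard infusion: 3% of the dose in hour 1, the remaining 97% over the next 3 hours (Protocol 7.4.6).
- Cohort 2 planned dose: 10 mg/kg, 3 patients, 24 weekly infusions each (SAP 4.1 and 14.1), hence 3 × 24 = 72 infusions.
- Stop times of 1, 2 and 3 hours are illustrative. The documents report no actual stops.

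**Formulas**
- SAP dose = added mL × 20.
- Delivered dose = added mL × 20 × f, where f is the fraction of the bag infused.
- f(t) = 0.03t for t ≤ 1 h; f(t) = 0.03 + 0.97(t − 1)/3 for 1 < t ≤ 4 h.

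**Per infusion.** The example uses an assumed 15 kg child at 10 mg/kg: 150 mg, which is 7.5 mL added.

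| Stop at | f | Delivered, mg | Delivered, mg/kg | SAP, mg/kg | SAP ÷ delivered |
|---|---|---|---|---|---|
| 1 h | 0.030 | 4.5 | 0.30 | 10 | 33.3 |
| 2 h | 0.353 | 53.0 | 3.53 | 10 | 2.83 |
| 3 h | 0.677 | 101.5 | 6.77 | 10 | 1.48 |
| 4 h (complete) | 1.000 | 150 | 10 | 10 | 1.00 |

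The last column is 1/f, so it does not depend on weight or dose level.

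**Effect on summaries of one 2-hour stop at 10 mg/kg**
- That visit, 3 patients: (10 + 10 + 3.53)/3 = 7.84 mg/kg.
- That patient, 24 infusions: (23 × 10 + 3.53)/24 = 9.73 mg/kg.
- The cohort, 72 infusions: (71 × 10 + 3.53)/72 = 9.91 mg/kg.

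The SAP formula gives 10 in each case. With three such stops among the 72 the cohort mean is (69 × 10 + 3 × 3.53)/72 = 9.73; with six it is (66 × 10 + 6 × 3.53)/72 = 9.46.

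**Clearance.** If CL takes the 8.4.8 dose, the numerator is the prepared dose while the AUC reflects the delivered dose. CL at that infusion is then overstated by 1/f, for example 2.83-fold after a 2-hour stop. This can arise only at infusions with a PK profile.

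**Choice of denominator.** Overfilled bags are run until empty, so dividing by the nominal 100 or 250 mL would give ratios above 1. If overfill were 5% to 10% (an assumed range), an emptied bag would give 1.05 to 1.10. The denominator therefore has to be the real bag volume.

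**The case against.** The strongest counter-argument is that the error depends on an eCRF form that is not shown. SAP 8.4.8 introduces the added volume as part of what was administered, and SAP 14.1 refers to SOBI003 volume without the word added. If the field already holds the amount infused, the formula is correct. That possibility stands, but it conflicts with Protocol 7.4.6, where added volume goes into the bag, and it sits poorly with two separate volume items in 14.1. Even on that reading, 8.4.8 needs a sentence to say so.

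Second, no abandoned infusion is documented. The protocol allows a reaction to be handled by prolonging the infusion, a recorded stop may be temporary, and all six patients went on to the extension study. This limits the likely frequency; it does not exclude single incomplete infusions.

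Third, the raw volumes and stop reasons are listed. With at most 6 × 24 = 144 planned infusions, a reader could find a partial one by hand. That is true, but the derived variable and its summary would still be wrong.

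Fourth, the PK effect is uncertain. Neither 15.5.4 nor 15.7 refers to 8.4.8, total dose could be computed from dose level and weight, the power model's critical interval is set from nominal dose levels, and unreliable PK parameters are flagged and excluded. All of this stands, so the PK point is conditional.

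Finally, the visit-level figure assumes that exposure is tabulated by visit. SAP section 8 sets that as the general rule, although the title of Table 14.3.4.7.1 does not confirm it.

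**Conclusion.** The concern holds. As written, 8.4.8 derives the prepared dose, 14.1 reports it as the actual dose, and nothing in either document corrects it for an incomplete infusion. The error is large for an affected infusion (3% to 68% delivered for stops at 1 to 3 hours, against 100% credited) and clear in a three-patient visit mean (7.8 against 10 mg/kg). It is small in the cohort average (9.9 against 10 for one 2-hour stop).

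These sizes assume a permanent stop on the standard 4-hour profile. They also assume that added volume carries the protocol's meaning in the eCRF. The realised effect is unknown because the number of abandoned infusions is not given. The primary adverse event tables are unaffected, and completed infusions, including slowed or paused ones, are counted correctly. The derivation should be corrected before the exposure table is produced.

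**What to change.** In SAP 8.4.8, define dose received (mg) = added SOBI003 volume × 20 × (infusion volume administered ÷ total prepared bag volume including overfill), and divide by bodyweight for mg/kg. Take the bag volume from the protocol's bag-concentration calculation or the accountability records, not the nominal 100 or 250 mL. Set the ratio to 1 when the bag was emptied. Keep added volume × 20 as a separate variable labelled dose prepared. In 15.5.4 and 15.7, state that the delivered dose is used for CL and for any analysis on actual dose. If the eCRF's SOBI003 volume field already means the amount infused, say that in 8.4.8 instead.

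The cost is one derivation for six patients, applied only to incomplete infusions. The drawback is that the prepared bag volume is not shown to be an eCRF field, so it may have to be retrieved from pharmacy or accountability records for those infusions.

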8.4.9 Time since diagnosis

Time since diagnosis will be calculated as ([date of 1st infusion – date of diagnosis]+1)/30.4373 and presented in months. In case of partial/missing date of diagnosis, time since diagnosis will not be calculated.

9 Patient disposition

An overall summary of patient disposition by dose cohort will be displayed for all screened patients with the numbers and percentage of patients screened, screen failures, treated, and included in the analysis sets. Additionally, the numbers and percentage of patients who completed study and were withdrawn from the study will be summarized, including the reason for study withdrawal. All data, including the reasons for screen failure and reasons for exclusion from each of the analysis sets, will be listed.

All protocol deviations identified will be summarized and listed.

Violated inclusion criteria and fulfilled exclusion criteria will also be listed.

10 Demographics and baseline characteristics

Demographic and other baseline characteristics will be summarized by dose cohort with descriptive statistics using the SAF.

10.1 Demographics and baseline characteristics

Date of birth, gestational age at birth, gender, ethnicity, race, country of residence and native language will be captured at Screening. In addition, information on the patient's siblings is captured, including age and MPS IIIA diagnostic status (confirmed as nonaffected/ confirmed as affected/under current investigation) (3). For sibling(s) with confirmed diagnosis, the sibling's age at diagnosis and genotype are also captured, when known.

For patient data, the following variables will be summarized: Age at first infusion (derived), gestational age at birth, gender, baseline weight, ethnicity, race, country of residence and native language. The same variables will be also included in listings, as well as date of birth.

For patient's siblings' data, the following variables will be summarized: Age (derived), MPS IIIA diagnostic status, and age at confirmed diagnosis. The same variables will also be included in listings, including also the genotype of siblings with confirmed diagnosis.

10.2 Medical history

For all medical history data, a frequency table of the number and percentage of patients will be provided by system organ class (SOC) and preferred term (PT) for each dose cohort. Tables will be sorted alphabetically by SOC and PT.

All medical history data will be coded using the latest version of the medical dictionary for regulatory activities (MedDRA), all data will be listed.

10.2.1 MPS IIIA diagnosis

Information on diagnosis date and prior MPS IIIA diagnostic procedures will be captured in the eCRF including assessment date, diagnostic method used and test result. Summary statistics will be presented for diagnostic status and time since diagnosis (defined in [9.4.9](#)). All data will be listed.

11 Prior and concomitant medication

Prior medications will be defined as any medications taken prior to the date of 1st study treatment. Concomitant medications will be defined as medications ongoing or with a start date on or after the date of the 1st study treatment or a stop date on or after the date of the 1st study treatment.

All prior and concomitant medication will be coded using the latest version of world health organization drug dictionary (WHO-DD). Data will be listed and summary tables will be presented by anatomical therapeutic chemical classification [ATC] level 4, and WHO-DD preferred term using the SAF.

Prior to each infusion of SOBI003, a single dose of non-sedative antihistamine will be administered. Antihistamine administration including date and time, medication name, dose, unit and route will be listed and summarized per visit.

For patients continuing in the extension study (SOBI003-002), any medications with onset after the 1st dose of study drug in the extension study will not be presented in the tables and listings of the FIH study (SOBI003-001) but in the tables and listings of the extension study.

12 Treatment compliance

There will be no measurement of, or analysis of, treatment compliance, nor does it affect population assignment (patients must be exposed to study drug to qualify for the analysis sets).

13 Efficacy analyses

Efficacy data will be summarized descriptively by dose cohort, visit, and time point using the FAS.

13.1 Questionnaires and scales

The patient's chronological age in combination with the patient's adaptive behavior age-equivalent score as established by VABS-II, will determine which neurocognitive test(s) to apply. The algorithm in **Table 5** is applied and the test(s) administered at Baseline should also be used at Week 24.

Table 5 Selection of neurocognitive assessment method

Chronological age at the assessment time point	VABS-II adaptive behavior age-equivalence	Neurocognitive test to apply
<42 months	Any age-equivalence	BSID-III
≥42 months	<36 months	BSID-III
≥42 months	36 to 42 months	BSID-III + KABC-II*
≥42 months	>42 months	KABC-II

* The BSID-III should be administered first, and there should be at least 2 days until the KABC-II assessment in order to reduce KABC-II outcome bias of patient tiredness.

13.1.1 VABS-II

For this study, the VABS-II assesses adaptive behavior in 4 competence domains (communication, socialization, daily living skills, and motor skills). The domain scores yield an adaptive behavior composite of the 4 domains (4). The VABS-II is assessed by parent/caregiver interviews performed by child development specialists/ psychologists with prior experience of MPS IIIA patients. A series of age-equivalent questions obtains a decreasing score between "4" and "0" or "DK" (don't know) based on how independently the individual is able to perform the behavior (i.e., 4 = "performs almost always independently", 0 = "never performs/never performs independently") is answered. The developmental age at Screening will be determined as the mean of the subdomain AEQ scores including the communication, socialization, daily living skills, and motor skills domains

The adaptive behavior AEQ and composite score will be obtained with the mean of the subdomain scores communication, socialization, daily living skills and motor skills for patients aged up to 6 years and 11 months. For patients aged 7 years and above, the adaptive behavior composite score will be obtained with the 3 subdomain scores communication, socialization, and daily living skills.

The VABS-II will be assessed at Screening, Baseline (within 2 weeks prior to 1st SOBI003 infusion) and at Week 24 (see **Table 1**). Each patient's parent/caregiver should preferably have the same interviewer throughout the study in order to reduce potential variability. Completed

assessment forms will be sent to a central reader (NeuroCog Trials), for data quality assurance of completed assessment forms, calculation of final scores and determination of AEq scores, and data management.

Changes from baseline (as defined in Section 8.4.3) will be calculated at Week 24.

13.1.2 **BSID-III**

The BSID-III is a standard series of measurements used primarily to assess the development of infants and toddlers. Children are assessed in the 5 key developmental subtests of cognitive, language, social-emotional, motor and adaptive behavior (5). For each developmental subtest the patient must respond to a series of questions with a score of “1” or “0” based on the successful completion (“1”) of a task. Total raw scores for each subtest can be obtained by adding all scores of the questions in the subtest.

The BSID-II will be assessed at Baseline (within 2 weeks prior to 1st SOBI003 infusion) and at Week 24, if applicable (see Table 1). Each patient should preferably have the same assessor throughout the study in order to reduce potential variability.

Changes from Baseline (as defined in Section 8.4.3) will be calculated at Week 24.

13.1.3 **KABC-II**

The KABC™-II is a standardized test that assesses intelligence and achievement in children. The test is comprised of four global test scores that include: sequential processing, simultaneous processing, achievement and mental processing (6). Each of the global tests contains a number of subtests with several questions. For each question, the patient must respond with a categorical score (mostly between “2” and “0”, but between “4” and “0” for some subtests), based on the difficulty that the patient experiences while answering the question (e.g., a difficult task would be scored with “0” and an easy task would be scored with “2” or “4” depending on the subtest).

A cumulative raw score can be obtained then for each subtest by adding the scores for each question in the subtest. Raw scores can be then transformed to adjusted scores and AEq.

The nonverbal index (NVI) of KABC-II is defined by adding certain subtests and based on the age of the patient. For patients between 3-6 years (cognitive age) it includes the subtests: conceptual thinking, face recognition, story completion, triangles, pattern reasoning and hand movements.

The KABC-II will be assessed at Baseline (within 2 weeks prior to 1st SOBI003 infusion) and at Week 24, if applicable (see Table 1). Each patient’s parent/caregiver should preferably have the same assessor throughout the study in order to reduce potential variability.

To ensure that the KABC-II assessments are performed in accordance with the study instructions, completed assessment forms will be sent to a central reader (NeuroCog Trials) for data quality assurance, calculation of final scores and determination of AEq and DQ scores.

Changes from Baseline (as defined in Section 8.4.3) will be calculated at Week 24.

